2. STUDY OBJECTIVES

- To determine the effects of consuming 9 oz of the Impossible BurgerTM, grass-fed beef or grain-fed beef on 300 min postprandial plasma inflammatory markers (IL-6, TNF-α, C-reactive protein, and VCAM-1).
- o To determine effects on plasma metabolites (vitamin and mineral derivatives, phenolics, amino acids etc.) collected through regular urine sampling during the 300 min postprandial phase (at 60 min, 180 min, and 300 min).
- o To determine the effects on subjective satiety at 30, 60, 90, and 120 min and every hour thereafter following consumption.

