Metabolic visits (Weeks 2-4. Number of Visits: 3. Duration: 7 hours each): These three visits will take approximately 7-hours each and will take place at The Center for Human Nutrition Studies (CHNS). Visits will be at least 3 days apart. Participants are required to fast for 12 hours prior to reporting to the laboratory. During this, participants will complete the following:

- Meat consumption: Using a randomized cross-over design, participants will ingest 250 g (9 oz) of an Impossible BurgerTM burger (plant), a grain-fed beef burger (grain-fed), a grass-fed beef burger (grass-fed). The meat will be stored as 9 oz. (250 g) patties in designated food freezers (-40 °C) in the NDFS kitchen and thawed overnight in a refrigerator (4 °C) prior to the subject's arrival the next morning. The meat will be cooked on a griddle in the CHNS metabolic kitchen on each side until an instant-read meat thermometer registers an internal temperature of 160 °F (71 °C). The patties will then be immediately served to the participant. Participants are provided with a standardized amount of water (1.5 liters) to drink during the 300 min post-meal phase. Participants will be asked to eat and drink the water at a comfortable rate but to try and finish within 30 min. No other food is allowed to be consumed during the ensuing 300 min postprandial phase. No other liquids are allowed to be consumed during that time as this would interfere with our protocol (see urine collection below). Subjects are also expected to remain seated in a chair during this time and can work/read/or watch entertainment on their own electronic device. Participants will be allowed to get up and use the rest-room; however, we will ask participants to remain sedentary otherwise.
- o **Blood Draws:** An intravenous catheter (IV) will be temporarily placed into a forearm or hand vein by a trained member of the study team (the PI) to collect repeated blood samples. The catheter will remain viable by a slow drip of saline. We will collect four samples total (10 mL each; 40 mL or 2 ½ tablespoons) on each of the three metabolic visits. One sample will be collected right before participants eat and three more samples will be collected at 60, 180 min and 300 min after they consume the meal. These draws will be taken in a private room in clinical facilities, in a reclining leather chair. Participants will be provided with their

Version 1 Page 5 of 9

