clinical lab results that will be obtained from LabCorp. Results from bloodwork will be shared with participants via encrypted email using a USU email account.

- O Urine Collection: A baseline urine sample will be collected prior to food consumption. Participants are asked to completely empty their bladder prior to food consumption. After food consumption, all urine will be collected in a urine jug (a 3000 mL urine collection bottle) during the 300-minute postprandial phase to study metabolites in the urine. All urine collections will be done by the participant themselves in private restroom facilities.
- Satiety Scale: Participants are asked to mark a satiety scale (Holt et al., 1995) at 30, 60, 90, 120 min, and every hour thereafter until 300 min to assess subjective satiety after meat consumption.

Dietary and activity control: We will ask participants to maintain their habitual diet, physical activity, and sleep levels. We will ask participants to fill in 3-day dietary and sleep logs for the three days prior to their metabolic visit (see attachments). We will also ask them to refrain from alcohol and strenuous physical activity (running, weightlifting etc.) for 2 days prior to each metabolic visit. The dietary and sleep logs will give us insight if lifestyle factors leading up to each visit were similar and are likely to promote compliance to ensure robust biomarker results (inflammatory cytokines and metabolomics). Participants are asked to replicate their 3-day foods logs and sleep schedule as much as possible prior to each visit. Participants are also asked to not consume red meat or soy (main ingredient of plant burger) the day before each visit. This is done to minimize any prior presence of common red meat and soyderived metabolites in the urine.

Table 2. Schedule of sample collection

Lab/Blood Work	Screening	Met Visit 1	Met Visit 2	Met Visit 3
Pregnancy test (hCG)	X			
Insulin	X			
Glucose	X			
BMP	X			
Lipid panel	X			
HbA1C	X			
Blood inflammatory markers		X	X	X
Urinary/plasma metabolomics		X	X	X

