4. SUBJECT RECRUITMENT AND COMPENSATION

4.1 Recruitment

Subjects will be recruited by posting flyers in designated areas around USU's campus, through advertisements on social media. In the advertisement, potential subjects for this study will be directed to contact the study team by email or phone to obtain more information about the study, if interested. Participants who are interested will be provided with a copy of the informed consent by email. When the participant expresses interest in being in the study, the study team member will confirm by telephone that the participant meets most of the inclusion/exclusion criteria (ones that can be determined without

Version 1 Page 6 of 9

the need for a blood draw) before scheduling him/her for a consent meeting. Subjects will attend a one-on-one information session that will be conducted by trained member to present the details of the study. We anticipate that we will need to telephone screen, approximately 150 people and that approximately 45 will be consented. We will enroll up to 30 participants to meet our goal of having at least 24 participants complete the study (assuming a 20 % drop-out rate).

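### Satiety is a stated objective but is never rated before the meal; one 0-min mark per visit would supply the missing baseline at almost no cost

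*Combined protocol and SAP*

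**What the plan says.** Section 2 (Study Objectives) lists the effect of the three meals on subjective satiety "at 30, 60, 90, and 120 min and every hour thereafter following consumption". Section 3.3 (Satiety Scale) repeats the schedule: "at 30, 60, 90, 120 min, and every hour thereafter until 300 min to assess subjective satiety after meat consumption". Neither place has a time 0.

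The other outcomes at the same visits do have one. For blood: "One sample will be collected right before participants eat". For urine: "A baseline urine sample will be collected prior to food consumption".

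The starting state is standardised indirectly. On fasting, section 3.3 says "Participants are required to fast for 12 hours prior to reporting to the laboratory". Participants are also asked to repeat their food and sleep pattern before each visit, and "The dietary and sleep logs will give us insight if lifestyle factors leading up to each visit were similar".

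Section 7 (Statistical analysis) plans change scores for the inflammatory biomarkers and metabolites. It names no summary or comparison for satiety.

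**The concern.** Among the outcomes followed through the post-meal period, satiety is the only one without a pre-meal value. Two things are lost: how far each meal moved satiety from the fasting state, and a direct measure of how hungry the participant was on arrival. The fast and the logs limit visit-to-visit differences and allow an indirect check on them, but they do not measure hunger.

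The first planned rating cannot fill the gap. Participants are asked to "eat and drink the water at a comfortable rate but to try and finish within 30 min". Whether the clock starts at the first bite or at the end of the meal, the 30-min rating reflects the meal.

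A rating not taken before the meal cannot be recovered later, so the decision has to be made before visits take place.

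**Working it through.** **Count of ratings.** The times are 30, 60, 90, 120, 180, 240 and 300 min: 7 per visit and 3 × 7 = 21 per participant, none pre-meal. A 0-min rating makes it 8 per visit and 24 per participant.

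**The plan's own figure.** Section 4.1 states "our goal of having at least 24 participants complete the study", and section 7 recruits 30 allowing for 20% drop-out: 24 / (1 − 0.20) = 30, which reproduces. That number was set for metabolomics. The documents give no power figure for satiety.

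**Assumptions.** There are 24 completers, 4 in each of the 6 possible meal orders, and two-sided alpha is 0.05. The documents give neither the sequences nor the sidedness. Let r be the within-person correlation, across visits, between the 0-min rating and the post-meal summary, and k the ratio of pre-meal to post-meal within-person SD. Neither is given, so both are varied. All SDs below are within-person.

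**Degrees of freedom.** There are 24 × 3 = 72 visit summaries. Person, period and meal together have rank 24 + 2 + 2 = 28, leaving 44 residual df. The 0-min covariate takes one more, leaving 43. With fixed person effects, a sequence term or a person-mean baseline term adds no rank.

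**Chance imbalance in starting hunger.** The SE of a difference between two meals is √(2/24) = 0.289 SD, so the 95% range is ±1.96 × 0.289 = ±0.566 SD of the pre-meal rating. The part expected to pass into the post-meal contrast is r × 0.566, in post-meal SDs:

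- r = 0: 0
- r = 0.3: ±0.17
- r = 0.5: ±0.28
- r = 0.6: ±0.34

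This is random error already contained in the ordinary standard error. It is not bias.

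**Reference effect.** With 44 df, 80% power needs a difference of 0.827 SD. A paired t-test on two meals (23 df), the method section 7 names for its other outcomes, needs 0.845 SD and has 78.3% power at 0.827.

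**Effect of a 0-min rating.** Relative to post-meal ratings alone, the variance of the contrast is 1 − r² with the covariate (before the lost df) and 1 + k² − 2rk with a plain change score. Power at 0.827 SD, from 20,000 simulated trials per setting:

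| r | 1 − r² | Covariate, k = 1 | Covariate, k = 0.5 | Change score, k = 1 | Change score, k = 0.5 |
|---|---|---|---|---|---|
| 0 | 1.00 | 79.4% | 79.3% | 51.1% | 70.9% |
| 0.3 | 0.91 | 83.3% | 82.4% | 66.0% | 81.9% |
| 0.5 | 0.75 | 89.2% | 89.2% | 79.9% | 89.9% |
| 0.6 | 0.64 | 93.4% | 93.0% | 88.0% | 93.4% |

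Rescaling a covariate does not change its fit, so k should not affect the covariate columns; they differ by less than 1 point. The change score is different: setting 1 + k² − 2rk = 1 gives break-even at r = k/2, which is 0.5 when k = 1 and 0.25 when k = 0.5.

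**Check on bias.** The unadjusted analysis recovered a mean estimate of 0.825 to 0.830 for a true 0.827, with type I error of 4.6% to 5.3%.

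**The case against.** The strongest reply is that no stated aim goes unmet. The objective asks about satiety at listed times after eating, the procedure collects exactly those times, and nothing promises a change from fasting for satiety. That stands, and it is why this is an improvement and not an error.

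Second, the gain in precision depends on an unknown r. The 12-hour fast and the replicated diet and sleep could narrow variation in hunger and make r small. In simulation at k = 1, covariate power was 79.4% at r = 0.1, 80.1% at 0.15 and 80.2% at 0.2, so break-even lies near 0.15 and the gain below 0.2 is negligible. This also stands. The worst case, though, is a loss of about 1 percentage point, and the rating still makes change from fasting reportable.

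Third, a participant without 0-min ratings cannot enter a covariate model, so a change made after enrolment starts needs a rule. That is fair, and the fix below includes one.

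Fourth, a single time-averaged summary is a choice, and the absence of a satiety analysis in section 7 is a separate matter of detail. Both are true; the same edit can settle them.

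Finally, the satiety form is not among the documents. If it already carries a pre-meal mark, sections 2 and 3.3 need only say so.

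**Conclusion.** The point holds as a low-cost improvement. Sections 2 and 3.3 schedule no pre-meal satiety rating, and nothing else in the plan measures starting hunger. The randomised within-person comparison of post-meal ratings remains valid and answers the objective as worded.

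What is lost is certain in one respect and uncertain in the other. Change from fasting cannot be reported at all. The lost precision ranges from nothing at r = 0 to the difference between 80% and about 93% power at r = 0.6. These figures assume 24 completers in balanced sequences and a two-sided 5% test. The documents support no particular r, so the higher power figures should not be read as expected values.

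**What to change.** - **Sections 2 and 3.3:** add a 0-min satiety rating at all three visits, taken with the baseline blood sample and before the patty is served.
- **Section 7, summary:** name one satiety summary per visit, for example the time-averaged area under the curve over 30–300 min. Trapezoid weights for the seven times are 15, 30, 30, 45, 60, 60 and 30, divided by their total of 270 min. Ratings at each time can be shown alongside.
- **Section 7, model:** compare the three meals in a crossover model with person, period and meal, and the 0-min rating as covariate. With fixed person effects, no sequence or person-mean term is needed.
- **Section 7, reporting:** give 0-min ratings by meal and change from 0 min descriptively. Do not make a plain change score the main analysis, because whether it gains or loses power depends on r and k, both unknown.
- **If visits have already taken place:** state in advance that the unadjusted 30–300 min summary in all participants is the main comparison. The covariate model is then supporting, in those with all three 0-min ratings.

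The cost is three extra marks per participant and a few sentences in section 7, with no added visit or sample. If r is near zero, the covariate costs about 1 percentage point of power (residual df 44 to 43).

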4. SUBJECT RECRUITMENT AND COMPENSATION

4.1 Recruitment

Subjects will be recruited by posting flyers in designated areas around USU's campus, through advertisements on social media. In the advertisement, potential subjects for this study will be directed to contact the study team by email or phone to obtain more information about the study, if interested. Participants who are interested will be provided with a copy of the informed consent by email. When the participant expresses interest in being in the study, the study team member will confirm by telephone that the participant meets most of the inclusion/exclusion criteria (ones that can be determined without

Version 1 Page 6 of 9

the need for a blood draw) before scheduling him/her for a consent meeting. Subjects will attend a one-on-one information session that will be conducted by trained member to present the details of the study. We anticipate that we will need to telephone screen, approximately 150 people and that approximately 45 will be consented. We will enroll up to 30 participants to meet our goal of having at least 24 participants complete the study (assuming a 20 % drop-out rate).

4.2 Compensation

Participants will receive compensation for completing each study procedure for a maximum of \$475, which will be paid at the end of the study. If a participant drops out of the study before completing the entire study, they will be paid according to the degree of completion. Participants will receive \$25 for the screening blood draw visit and \$150 for each of the metabolic visits.

5. RISK/BENEFIT ASSESSMENT

This study provides no potential benefit to the participant other than the satisfaction of having contributed to the potential future benefit of others. Participants will be provided with their lab clinical results, which may be of interest to them. Society may benefit by having more information about the health effects of different types of meat, which may help inform consumer food choices. Participation in this study may lead to increased risk for the following:

o **Blood draws:** Blood drawing can result in bruising, mild discomfort, and rarely, an infection where the needle enters the skin. There also is a possibility of lightheadedness and fainting. Sterile techniques and the use of trained phlebotomists will minimize these risks.

6. COSTS TO THE SUBJECT

There will be no costs to participants for any of the treatments or testing done as part of this research study. Immediate necessary care is available if an individual is injured because of participation in a research project. However, there is no provision for free medical care or for monetary compensation for such injury. During this study, hospitalizations or additional care beyond the scope of this study will be the responsibility of patients and/or their insurance company.

7. ANALYTICAL PROCEDURES AND STATISTICAL CONSIDERATIONS

- o **Inflammation:** Inflammatory biomarkers (IL-6, VCAM-1, TNF-alpha and C-reactive protein [CRP]) will be measured using ELISA kits at Dr. [name]'s laboratory at Utah State University. Plasma samples will be stored at -80°C until cytokine analyses are performed.
- Metabolomics: Mass spectrometry techniques will be used for untargeted and/or targeted assessment of blood and/or urinary metabolites. This analysis will give insight into the appearance of food-derived metabolites in the human body and how they may impact inflammatory responses after eating. This analysis will be performed using de-identified samples by Metabolon Inc (a company dedicated to metabolomics analysis) and/or the Plant for Human Health Institute. Samples will be provided to these core services as de-identified samples. No other data will be shared with these core services. Plasma and urine samples will be stored at -80°C until metabolomics analyses are performed.

Version 1 Page 7 of 9

- o **Dietary logs:** The Diet History Questionnaire III (NIH) and 3-day food records will be analyzed by dietetic staff within Dr. [name]'s laboratory at Utah State University.
- Statistical analysis: Change scores (post-dietary intervention baseline) will be created for all inflammatory biomarkers and metabolites. Metabolic intermediate data will be reduced into Metabolic Factors using Principal Component Analysis (PCA) of the change scores. Factor scores will be computed for each individual for both diets. Change scores and factor (change) scores for both diets will be compared using paired t-tests. P< 0.05 will be considered statistically significant and analyses will be performed in SAS 9.4 (SAS, Cary, NC).

- o **Power Calculations:** Using untargeted metabolomics for our power calculations of the number of participants we need to recruit, we assume a P-value ≤ 0.05, Q-value ≤ 0.3, and standard deviation of 0.3 based on previous work (Pimentel et al., 2018). Since there are no entirely comparable previous studies available to draw from, the effect size and number of truly different metabolites are meant to give general estimates. 600 metabolites are typically identified (Nieman et al., 2015) and conservative estimation is that 20-40 metabolites will be significantly different with a mean of 0.2624 (30% difference). An n=24 per group is expected to provide true discovery rates ranging from 89-93 % assuming differences in 80-120 metabolites. Assuming a drop-out of 20%, the final number of participants we will recruit is N=30. This, we consider adequate without having to engage more participants than necessary to address the research aims.

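### Change scores by paired t-test are valid but fix the pre-meal weight at 1 and leave scale and post-meal time open; a log model with the pre-meal covariate is a cheap improvement

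*Combined protocol and SAP*

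**What the plan says.** Section 7 (Statistical analysis) sets the outcome: "Change scores (post-dietary intervention baseline) will be created for all inflammatory biomarkers and metabolites". I read this as post-meal value minus baseline. The test follows: "Change scores and factor (change) scores for both diets will be compared using paired t-tests". No transformation, covariate or post-meal time is named.

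Other parts of the document bear on these gaps:

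- **Scale.** Section 7 (Power Calculations) says: "conservative estimation is that 20-40 metabolites will be significantly different with a mean of 0.2624 (30% difference", with a "standard deviation of 0.3 based on previous work". It does not say what quantity that SD describes.
- **Time.** Section 3.3 (Blood Draws) schedules one pre-meal plasma sample, and "three more samples will be collected at 60, 180 min and 300 min after they consume the meal". The first objective in section 2 refers to effects of "grass-fed beef or grain-fed beef on 300 min postprandial" plasma inflammatory markers. That may mean the 300 min sample or the whole phase; the next objective uses 300 min for the length of the phase.
- **Urine.** The second objective in section 2 is labelled plasma metabolites, yet lists 60, 180 and 300 min under urine sampling. Section 3.3 (Urine Collection) takes a pre-meal sample and pools all post-meal urine in one jug. On fluid intake, section 3.3 says: "Participants are provided with a standardized amount of water (1.5 liters) to drink during the 300 min post-meal phase". No volume or dilution rule is given.
- **Fluid analysed.** Section 7 (Metabolomics) leaves this open: "untargeted and/or targeted assessment of blood and/or urinary metabolites".

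**The concern.** A change score subtracts the whole pre-meal value, noise included. When sample noise is a large part of the within-person variation, a weight below 1 gives a more precise meal contrast. The pre-meal sample is already drawn at each visit, so the data could set that weight at almost no cost.

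The second issue is prespecification. A change at 60, 180 or 300 min, or over the phase, on the raw or the log scale, would each satisfy section 7. If the choice were made after seeing results, the nominal 5% level would no longer hold. The planned 30% effect would also be tested on a scale other than the one used to plan it if raw differences were analysed.

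**Working it through.** **The plan's own figures.** ln(1.30) = 0.2624 matches the planned effect; log2(1.30) = 0.3785 and log10(1.30) = 0.1139 do not. So the metabolite effect was planned in natural logs. The recruitment figure, 24/(1 - 0.20) = 30, also reproduces. Neither is disputed here.

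**Inputs.** From section 7: n = 24, effect 0.2624, SD 0.3, P < 0.05 (taken as two-sided; the plan does not say). Not in the documents, so assumed: the within-person log-scale SDs for visit-to-visit level (v), sample noise (e) and meal response (s).

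**Variances.** Take the difference between two meals within a participant, so that stable between-person differences cancel.

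- Change score: 2(2e² + s²).
- Adjusted for the pre-meal difference: 2[v² + e² + s² - v⁴/(v² + e²)], times (n - 2)/(n - 3) = 22/21 for estimating the slope.

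Example with v = e = 0.2 and s = 0. Change score: 2 × 0.08 = 0.16. Adjusted: 2[0.08 - 0.0016/0.08] = 0.12. Ratio: 0.12/0.16 × 22/21 = 0.79.

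| v | e | s | Change-score variance | Adjusted variance (before 22/21) | Ratio (with 22/21) | Simulated power, change → adjusted |
|---|---|---|---|---|---|---|
| 0.2 | 0.2 | 0 | 0.16 | 0.120 | 0.79 | 87 → 93% |
| 0.4 | 0.2 | 0 | 0.16 | 0.144 | 0.94 | 87 → 89% |
| 0.2 | 0.3 | 0 | 0.36 | 0.235 | 0.69 | 53 → 69% |
| 0.4 | 0.3 | 0 | 0.36 | 0.295 | 0.86 | 53 → 60% |
| 0.2 | 0.2 | 0.2 | 0.24 | 0.200 | 0.87 | 71 → 76% |
| 0.4 | 0.1 | 0.3 | 0.22 | 0.219 | 1.04 | 75 → 73% |

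Type I error was about 5% for both methods.

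**General form.** Let r be the within-person pre/post correlation and k the ratio of post to pre SD. The variances are proportional to k² + 1 - 2rk (change) and k²(1 - r²) × 22/21 (adjusted), and the best weight is rk. With k = 1 the ratio is (1 + r)/2 × 22/21, so adjustment wins below r = 2 × 21/22 - 1 = 0.91. When rk is near 1, the change score is ahead by at most about 5% in variance.

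**Tied to the planned SD.** Suppose 0.3 is the SD of one meal's log change, so 2e² + s² = 0.09. The between-meal SD is 0.3 × √2 = 0.424, the noncentrality is 0.2624 × √24/0.424 = 3.03, and change-score power is 82.7%. With the covariate, power is 91% (v = 0.2) or 85% (v = 0.4) if all of that SD is noise, 84% or 82% at noise 0.15, and 81 to 82% at noise 0.1 or less. The range is about -2 to +8 points.

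**Three-meal model.** With 24 participants over six sequences and participant, period and meal in both analyses, the pattern is the same: 88 → 95% (v = e = 0.2, s = 0), 55 → 73% (v = 0.2, e = 0.3, s = 0) and 77 → 76% (v = 0.2, e = 0.1, s = 0.3).

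**Open time and scale.** With no meal effect and a between-person SD of 0.8, reporting the smallest p-value over the three times gives 12 to 13% false positives without response variation and 8 to 12% with response SD 0.2 to 0.3. On scale, at noise 0.2 and no response variation, the untransformed change has 64 to 69% power against 87% for the log change at between-person SD 0.8, but 82 to 86% against 87% at 0.3.

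**The case against.** The strongest reply is that nothing here is wrong with the planned test. It is unbiased for the meal contrast in a randomised crossover without carry-over, and it holds its level. A reader might infer that the change score is invalid, or that the covariate always helps; the documents support neither. The gain rests on SDs that the documents do not give, and on one reading of the only SD they do give it may be nil or slightly negative. That stands, and it is why this is an inexpensive improvement rather than an error.

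The scale comparison is also partly built in: the simulated data are log-normal with a multiplicative effect, so the log scale must win. For IL-6, TNF-alpha, CRP and VCAM-1 the documents give no effect, SD or distribution, so no planned figure is departed from.

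A reader might infer that the trial will report inflated false positives. Section 7 does not say that the most favourable time or scale will be chosen, so the inflated rates are conditional on such a choice.

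On urine, the second objective is labelled plasma metabolites and its times equal the blood-draw times, so a wording slip is likely. The passages still need reconciling.

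A reader might also infer, from the red-meat and soy restriction before each visit, that many pre-meal values fall below the assay limit and undermine log changes. The documents give no below-limit rate, and the restriction's stated aim concerns urine. One substitution rule is enough; a separate model for such metabolites is not warranted.

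**Conclusion.** The point holds as a recommended, low-cost improvement in efficiency and prespecification. The gaps in scale, post-meal time and urine sampling are facts of the text and need no assumed SD.

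The benefit of the covariate does depend on assumptions. For a two-meal contrast with n = 24 and a 30% effect, it is about +2 to +16 points at noise SD 0.2 to 0.3 without response variation. It is smaller when meal response varies between visits, and a loss of 1 to 2 points is possible when that variation dominates or the pre/post correlation is very high. Confidence in the size is moderate at best, because the documents report no pre/post correlation.

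**What to change.** Replace the change-score and paired t-test sentences in section 7 with a specification along these lines:

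- Plasma markers and metabolites are natural-log transformed, with one stated substitution rule for values below the assay limit.
- One main post-meal value per marker is fixed before data are seen: the 300 min sample, or the mean of the three log values if the first objective means the whole phase. Other times are secondary.
- The main value is analysed in a linear model with participant, period and meal as factors and the same visit's log pre-meal value as covariate. Meal contrasts are reported as geometric-mean ratios.
- PCA stays on log changes, at the same main time. Factor scores are already baseline-subtracted and need no baseline covariate.
- The fluid for metabolomics is stated: plasma, urine or both.

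Reconcile sections 2 and 3.3 on whether urine is sampled at three times or pooled. State one volume or dilution normalisation that can be applied to both the pre-meal sample and the pooled urine. No collection interval is given for the pre-meal sample, so a rate-based rule would require that interval to be recorded.

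Cost: wording, one degree of freedom for the covariate plus the period terms, results as ratios rather than absolute differences, and the possible 1 to 2 point loss above. No new samples are needed. Assaying every draw takes 24 × 3 × 4 = 288 plasma assays per marker, against 24 × 3 × 2 = 144 for baseline and one post-meal sample; this is extra only if not all draws were already to be assayed.
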